4.1.1. Adjustment for Covariates

The study is stratified by country/geographic region, OSA severity (not severe [AHI <30], severe [AHI \geq 30]), and gender. Unless otherwise specified, the following factors will be adjusted for: geographic region (US/OUS), OSA severity (not severe [AHI <30], severe [AHI \geq 30]), and gender. The value for stratification factors will be obtained from the data collected or derived from the eCRF or PSG results. In addition, the baseline value of the endpoint will be used as a covariate when appropriate.

4.1.2. Handling of Dropouts or Missing Data

For the primary and key secondary efficacy endpoint analyses aligned to the treatment regimen estimand and subject to Type 1 error rate control, missing data will be imputed based on the reason for the missing values, as described in [Table GPIF.4.2](#). For analyses aligned to the “efficacy” estimand, missing data will be considered missing at random and hence no explicit imputation will be performed.

For exploratory endpoints and safety analyses, missing values will not be explicitly imputed unless specified otherwise.

For analyses aligned to the treatment regimen estimand, the statistical inference over multiple imputations will be guided by the method proposed by Rubin (1987). The missing values will be handled as follows:

Table GPIF.4.2. Imputation Approaches to Handle Missing/Invalid Data for Treatment Regimen Estimand

| Missing/Invalid Data | Strategy to Handle Missing/Invalid Data | Assumptions for Missing Values | Methods to Handle Missing Values |
|--|---|--------------------------------|--|
| Data missing at baseline, invalid data collected or missing data after treatment DC due to the COVID-19 pandemic (after other reasons for missing data are ruled out), technical issues (that is, sensor error on PSG) leading to invalid measurements ascertained while on treatment, or missing data after study DC due to inadvertent enrollment. | Hypothetical | MAR | Multiple imputation assuming MAR |
| Missing data due to any other reason (for example, study DC due to any reason other than COVID-19 or inadvertent enrollment). | Treatment policy | MNAR | Retrieved dropout imputation ^a . If there are not enough retrieved dropouts to provide a reliable imputation model, placebo-based multiple imputation will be used. |

Abbreviations: COVID-19 = coronavirus disease-2019; DC = discontinuation; MAR = missing at random;

MNAR = missing not at random; PSG = polysomnography; SBP = systolic blood pressure.

^a Retrieved dropout imputation utilizes observed data from participants in the same treatment group who had outcome measures at Week 52 (or Week 48 for SBP) after early DC of study drug to impute the missing value.

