Fasting Visit		X	X	X	X	X	X	X	X	X	X	X	X	See footnote b.	
Physical Evaluation															
Height	X														
Weight	X	X	X	X	X	X	X	X	X	X	X	X	X	Weight measurements should be obtained per the instructions in Section 10.8.	
Waist circumference		X					X			X	X	X		Waist circumference should be obtained per the instructions in Section 10.8.	
Hip circumference		X					X			X	X	X		Hip circumference should be obtained per the instructions in Section 10.8.	
Neck circumference		X					X			X	X	X		Neck circumference should be obtained per the instructions in Section 10.8.	
Vital signs	X	X	X	X	X	X	X	X	X	X	X	X	X	Includes PR and BP. Measured after participant has been sitting at least 5 minutes. Vital-sign measurements should be taken before obtaining an ECG tracing and before collection of blood samples for laboratory testing. See Sections 8.2.2 and 10.8.	
Complete physical examination	X													The complete physical examination is performed (excludes pelvic, rectal, and breast examinations unless clinically indicated).	
Symptom-directed physical assessment		X (refer to Comment)												Symptom-directed physical assessment from V2 through V11 and ED will be conducted at the discretion of the PI, as indicated based on participant status and standard of care.	

	Study Period I - Screening	Study Period II - Treatment												Study Period III - Post-Treatment Follow-up	Comments
		2	3	4	5	6	7	8	9	10	11	ED			
Visit number	1												801		
Weeks from randomization	-4	0	4	8	12	16	20	24	36	48	52	-	See footnote a		
Visit interval tolerance (days)	-14 to +21	-	±3	±3	±3	±3	±7	±3	±7	±3	±7	±7	±3		
Fasting Visit		X	X	X	X	X	X	X	X	X	X	X		See footnote b.	
															May be performed by qualified personnel per local regulations.
12-lead ECG (local)	X											X	X		ECG measurements should be obtained per the instructions in Section 8.2.3.
Wearable Devices and PSG Assessments															
Schedule Sleep Center Study for PSG	X					X				X					PSG results must be reviewed to confirm eligibility prior to randomization.
Sleep Center Study for PSG	X					X				X					PSG at V7 and 11 may be scheduled for any day +/- 14 days.
Participant wears the WatchPat300	X		X	X	X	X				X					Applicable only to participants in GPII (off PAP). Training documents will detail information on the dispensation, wearing, and return process.

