| To demonstrate that tirzepatide at the MTD (10 mg or 15 mg) QW is superior to placebo for Change in exploratory PROs | From baseline to Week 52 Change in EQ-5D-5L utility index EQ-VAS scores Percent of participants with improved categorical shift in: PGIC-OSA Sleepiness PGIC-OSA Fatigue PGIC-OSA Sleep quality PGIC-OSA Snoring |
| To evaluate the effect of tirzepatide on sleep parameters as measured by Actigraphy (AX6) | Change from baseline to endpoint assessment in Daytime sleep duration Daily step counts Average acceleration |

Abbreviations: AHI = Apnea-Hypopnea Index; AX6 = Axivity 6; BP = blood pressure; DBP = diastolic blood pressure; ESS = Epworth Sleepiness Scale; EQ-5D-5L = EuroQol-5 Dimension-5-Level; EQ-VAS = EuroQol Visual Analogue Scale; FOSQ = Functional Outcomes of Sleep Questionnaire; HDL = high-density lipoprotein; hsCRP = high-sensitivity C-reactive protein; MTD = maximum tolerated dose; OSA = obstructive sleep apnea; PAP = positive airway pressure; PGIC-OSA = Patient Global Impression of Change – Obstructive Sleep Apnea; PGIS-OSA = Patient Global Impression of Status – Obstructive Sleep Apnea; PRO = patient-reported outcome; PROMIS = Patient-Reported Outcomes Measurement Information System; QW = once weekly; SASHB = sleep apnea-specific hypoxic burden; SBP = systolic blood pressure; SF-36v2 = Short-Form 36 version 2.

^a Subject to submission wide type 1 error rate control (Vandemeulebroecke et al. 2024).

b BP will be assessed at Week 48 because PAP withdrawal at Week 52 may confound BP assessment.

1.1.1. *Estimands*

Primary estimands

The primary and each key secondary efficacy analysis will be guided by the “*treatment regimen*” estimand and the “*efficacy*” estimand to support global regulatory submissions and publications. The “*efficacy*” estimand provides an on-treatment assessment of efficacy without confounding the treatment effect from the data collected after treatment discontinuation. It represents on-treatment efficacy. The “*treatment regimen*” estimand estimates the treatment effect, including the effect of intervention discontinuation to reflect clinical practice. It represents the efficacy irrespective of adherence to study intervention. The “*treatment regimen*” estimand will be used as the primary estimand to support a marketing application for the FDA.

Efficacy estimand

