The clinical question of interest for the efficacy estimand is the treatment difference between tirzepatide and placebo after 52 weeks of intervention in treated participants with obesity and OSA, prior to study intervention discontinuation for any reason.

Efficacy estimand attributes

- *Population:* Adult participants with obesity and OSA who received at least 1 dose of study treatment.
- *Treatment condition:* On randomized treatment.
- *Endpoints:* The primary and key secondary endpoints will be studied. Further details on the endpoints can be found in the Objectives and Endpoints table (Section 1.1).
- *Population level summary:* The difference in mean change from baseline to 52 weeks will be used for continuous endpoints; the difference in proportion (absolute or relative, as appropriate) will be used for dichotomous endpoints. The population level summary will be conducted using the EAS described in Section 3.
- *Handling of intercurrent events:* The intercurrent events of treatment discontinuation and use of PAP therapy for participants in ISA1 is addressed by the hypothetical strategy. The potential outcome of interest is the response in the efficacy measurement if participants would remain on their randomly assigned treatment for 52 weeks and would not initiate PAP therapy during the study.
- *Rationale:* The efficacy estimand provides an on-treatment assessment without confounding the treatment effect from off-treatment data.

Treatment regimen estimand

The clinical question of interest for the treatment regimen estimand is the treatment difference between tirzepatide and placebo after 52 weeks of intervention in treated participants with obesity and OSA, regardless of intervention discontinuation for any reason.

Treatment regimen estimand attributes

- *Population*: Adult participants with obesity and OSA who received at least 1 dose of study treatment.
- *Treatment condition*: On- or off-randomized-treatment.
- *Endpoints*: The primary and key secondary endpoints will be studied. Further details on the endpoints are in the Objectives and Endpoints table (Section 1.1).
- *Population level summary*: The difference in mean change from baseline to 52 weeks will be used for continuous endpoints and the difference in proportion (absolute or relative, as appropriate) will be used for dichotomous endpoints. The population level summary will be conducted using the FAS described in Section 3.

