**Figure GPIF.2.1****Graphical testing scheme for Study GPIF.**

3. Analysis Sets

Table GPIF.3.1 describes the populations that will be used for statistical analyses within each ISA of the master protocol. Additional intervention-specific populations for analyses may be described in the respective ISA.

Table GPIF.3.1. Description of Analysis Population

| Analysis Population | Description |
|---------------------------------|---|
| Entered | All participants who sign informed consent. |
| Randomized | All participants who are randomly assigned a study treatment (double-blind). |
| Modified intent-to-treat (mITT) | All randomized participants who are exposed to at least 1 dose of study intervention. |

Table GPIF.3.2. Description of Analysis Data Point Sets

| Analysis Set | Description |
|-----------------------------|---|
| Full analysis set (FAS) | Data obtained during treatment period of set of participants from the mITT population, regardless of adherence to study intervention. |
| Efficacy analysis set (EAS) | Data obtained during treatment period of set of participants from the mITT population, excluding data after discontinuation of study intervention (last dose + 7 days) and for ISA1, excluding data after initiating PAP therapy. |
| Safety analysis set (SS) | Data obtained during treatment and safety follow-up period of set of participants from the mITT population, regardless of adherence to study intervention. |

Abbreviations: EAS = efficacy analysis set; FAS = full analysis set; ISA = intervention-specific appendix; mITT = modified intent-to-treat; PAP = positive airway pressure; SS = safety analysis set.

4. Statistical Analyses

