4.3.1. Analysis Related to the Efficacy Estimand

The primary analysis guided by the "efficacy" estimand will be conducted using the EAS. This analysis will be based on the contrast between tirzepatide at the MTD (10 mg or 15 mg) and placebo at Week 52 (Visit 11) from the MMRM analysis of mean change from baseline in AHI. All the longitudinal observations at each scheduled postbaseline visit will be included in the analysis. REML will be used to obtain model parameter estimates and the Kenward-Roger option will be used to estimate the denominator degrees of freedom. The response variable of the MMRM will be the change in AHI from baseline values obtained at each scheduled postbaseline AHI measurement.

The model will include the fixed class effects of treatment, strata (geographic region [US/OUS] and gender), visit, and treatment-by-visit interaction, as well as the continuous, fixed covariate of baseline AHI. An unstructured covariance structure will be used to model the within-participant errors. Significance tests will be based on least squares means and Type III tests. If this analysis fails to converge, the following covariance structures will be tested in order until convergence is achieved:

- Toeplitz with heterogeneity
- autoregressive with heterogeneity
- compound symmetry with heterogeneous variances
- Toeplitz
- autoregressive, and
- compound symmetry without heterogeneous variances.

Analysis aligned to each estimand will be evaluated at the full significance level of 0.05.

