4.4.1.1. Main Analytical Approaches

Analysis of percent change in AHI, percent change from baseline to Week 52 in body weight, change from baseline to Week 52 in log of high-sensitivity C-reactive protein, change from baseline to Week 48 in SBP, change from baseline to Week 52 in PROMIS Sleep-related impairment, change from baseline to Week 52 in PROMIS Sleep disturbance, and change from baseline to Week 52 in log of hypoxic burden will be conducted in a manner similar to the primary efficacy analyses using an ANCOVA model with treatment, strata (geographic region [US/OUS], AHI stratum [not severe (AHI <30), severe (AHI \geq 30)], and gender), and baseline of the corresponding variable as a covariate for the treatment regimen estimand. If the hypoxic burden is reported to be 0, log (1) will be used in place of the log of hypoxic burden. The analysis method utilizing data from both ISAs for change from baseline to Week 52 in PROMIS sleep Impairment and PROMIS Sleep disturbance is described in the integrated efficacy analysis plan.

For the efficacy estimand, the MMRM analyses will be conducted as described in Section 4.1. For both estimands, analysis of percent change in AHI will adjust for the continuous, fixed baseline value of AHI instead of the baseline AHI stratum (not severe, severe).

Comparisons at the 52-week visit between the treatments relative to the proportion of participants achieving \geq 50% AHI reduction and AHI <5 or (AHI 5 through 14 and ESS \leq 10) will be conducted using logistic regression analysis including the following terms as a covariate:

- treatment
- geographic region (US/OUS)
- baseline AHI, and
- gender.

Unconditional risk differences will also be provided for these endpoints using logistic regression (Ye et al. 2023).

Analysis aligned to each estimand will be evaluated at the full significance level of 0.05 contingent on reaching statistical significance of the primary objective.

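### Under the efficacy estimand, the two binary AHI key secondaries fall to a Week 52 complete-case logistic regression that ignores Week 20 AHI, so it need not estimate the stated hypothetical effect

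*SAP*

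**What the plan says.** SAP Section 1.1.1 applies the efficacy estimand to the primary and every key secondary endpoint, dichotomous ones included. Treatment discontinuation and, in ISA1, PAP use are handled hypothetically, and the target is put this way: "The potential outcome of interest is the response in the efficacy measurement if participants would remain on their randomly assigned treatment for 52 weeks".

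The efficacy analysis set (Section 3, Table GPIF.3.2) is built by "excluding data after discontinuation of study intervention (last dose + 7 days) and for ISA1, excluding data after initiating PAP therapy". Section 4.1.2 then states, with no exception for binary endpoints, that "missing data will be considered missing at random and hence no explicit imputation will be performed". The imputation in Table GPIF.4.2 is confined to the treatment regimen estimand.

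AHI is measured after baseline at Week 20 and Week 52; the Protocol's Schedule of Activities notes that "PSG at V7 and 11 may be scheduled for any day +/- 14 days". For continuous AHI, SAP Section 4.3.1 uses both: "All the longitudinal observations at each scheduled postbaseline visit will be included in the analysis". For the two binary AHI key secondaries, Section 4.4.1.1 says that the Week 52 comparisons "will be conducted using logistic regression analysis including the following terms as a covariate". The listed terms are treatment, region, baseline AHI and gender. It adds: "Unconditional risk differences will also be provided for these endpoints using logistic regression".

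On scope, Section 1.1.1 says that the treatment regimen "estimand will be used as the primary estimand to support a marketing application for the FDA".

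**The concern.** The step from MAR to no imputation is sound for a likelihood-based MMRM, because the likelihood conditions on the observed Week 20 AHI. A single-visit logistic regression has no such mechanism. A participant without an on-treatment Week 52 outcome leaves the fit, and the Week 20 value leaves too. The logistic model therefore needs leaving to be unrelated to Week 20 response given treatment, region, baseline AHI and gender. That is stronger than MAR given the observed AHI data.

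The same AHI measurements would thus be analysed under two different missing-data assumptions for one estimand. The analysis set creates the missing outcomes by design, since it deletes values after treatment stops or, in ISA1, after PAP starts. Standardising the risk difference does not help, because it adjusts for baseline covariates only.

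Both endpoints are tested under the efficacy estimand's own full 0.05 graph (SAP Section 4.4.2). What is at stake is the size of the reported responder difference, in either direction.

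**Working it through.** **The plan's own figure.** SAP Section 5 gives a 50-point difference in percent change in AHI, SD 50, about 103 per arm and 25% dropout. Completers per arm: 103 × 0.75 ≈ 77. Standard error: 50 × √(2/77) = 8.06. Power: Φ(50/8.06 − 1.96) = Φ(4.25) ≈ 0.99999. The stated 90% or more reproduces as a lower bound.

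**Assumptions that are not in the documents.**
- Percent change is normal, with mean 0 on placebo and −50 on tirzepatide.
- The Week 20 to Week 52 correlation ρ is 0.6 to 0.8.
- The log-odds of leaving rise by b = 0.5 or 1 per SD worse Week 20 response (odds ratio 1.6 or 2.7).
- Between 0% and 50% of dropout occurs before Week 20 and is unrelated to response.
- Baseline covariates are unrelated to percent change, so the logistic fit reduces to observed proportions.

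**True values for at least 50% AHI reduction.** Tirzepatide Φ(0) = 0.5000; placebo Φ(−1) = 0.1587. The risk difference is 0.3413. With 77 per arm, a two-proportion test has power of about 0.997.

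**Complete-case rate.** Let z be the standardised Week 20 response (higher is worse), S(z) = 1 − expit(a + bz) the probability of staying, with a set to give the required dropout, and c = 0 (tirzepatide) or −1 (placebo). The rate among completers is

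∫ Φ((c − ρz)/√(1 − ρ²)) S(z) φ(z) dz ÷ ∫ S(z) φ(z) dz.

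**Worked case:** ρ = 0.7, b = 1, 25% dropout, all after Week 20. If poor responders leave, the completer rate is 0.5601 on tirzepatide and 0.1896 on placebo.
- Both arms: 0.5601 − 0.1896 = 0.3705, bias +0.029.
- Tirzepatide only: 0.5601 − 0.1587 = 0.4014, bias +0.060.
- Placebo only: 0.5000 − 0.1896 = 0.3104, bias −0.031.

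With half the dropout before Week 20, these become +0.018, +0.035 and −0.017.

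**Bias over the full grid:**

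| Who leaves | 25% dropout | 10% dropout |
|---|---|---|
| Unrelated to response | 0 | 0 |
| Poor responders, both arms | +0.01 to +0.03 | +0.003 to +0.015 |
| Poor responders, tirzepatide only | +0.02 to +0.07 | +0.006 to +0.028 |
| Poor responders, placebo only | −0.01 to −0.03 | −0.003 to −0.013 |
| Opposite direction by arm | −0.03 to −0.10, or +0.03 to +0.12 | not tabulated |

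A second simulation used correlations 0.4 to 0.8, slopes 0.7 and 1.4, a Week 20 effect 70% of the Week 52 effect, and all dropout after Week 20. Complete-case risk differences ran from 0.26 to 0.43. Imputation from Week 20 returned 0.34 throughout.

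**Trial-size check** (103 per arm, 1500 trials, 10 imputations, ρ = 0.7, all dropout after Week 20, normal data):
- Unrelated dropout: complete case 0.343 (SD 0.069), multiple imputation 0.341 (SD 0.062).
- Poor responders leave both arms: complete case 0.370 (SD 0.074), multiple imputation 0.341 (SD 0.065).
- Placebo only: complete case 0.311, multiple imputation 0.340.

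**Skewed AHI** (log-normal ratio bounded at −100%, true difference 0.552): complete-case bias was +0.01 to +0.04, +0.02 to +0.07 and −0.01 to −0.03 for both arms, tirzepatide only and placebo only. In the both-arms run, full data gave 0.551, complete case 0.586 and log-scale imputation 0.551. Raw-scale normal imputation gave 0.522 against full data of 0.550, and 0.513 against 0.554 when dropout was unrelated to response.

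**Remission composite** (assumed baseline AHI median 40, log-SD 0.5, at least 15; ESS mean 9 v 7, SD 4.5; true difference about 0.38): bias +0.02 to +0.04, +0.03 to +0.05 and about −0.01. Standardising over all treated participants rather than completers changed this by 0.001 or less.

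**The case against.** The strongest case against this point has five parts.

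- **The SAP never says complete-case.** It follows from a single-visit model with no imputation. Section 4.1.2 also does not say what its MAR assumption conditions on. Both observations are correct, but no section supplies another rule for these endpoints. The ISA2 sensitivity analysis (Section 4.4.1.2) censors more polysomnograms and returns to the same logistic model. The MMRM sentence in Section 4.4.3 covers supportive secondaries only.
- **Type I error is not generally at risk.** In the normal model with no treatment effect and the same dropout mechanism in both arms, the bias is exactly zero. Only arm-specific mechanisms distort the null. This stands.
- **The sizes rest on assumed inputs.** The 25% is a sample-size allowance, not a rate of treatment discontinuation, and Protocol Section 7.2 expects study withdrawal to be uncommon. If placebo improves by 20% and the 50-point difference is kept, the both-arms bias falls to between +0.003 and +0.016. Escalation takes 20 weeks, so early stopping could exceed half of all dropout. At a 75% early share the bias is at most +0.012 (both arms) or +0.022 (tirzepatide only). The both-arms bias is under half the sampling SD of about 0.07. All of this limits the size but does not remove the arm-specific cases.
- **Imputation can do harm.** Raw-scale normal imputation was biased by −0.03 to −0.05 in the skewed model even where complete case was not. This stands, and it determines how the imputation should be done.
- **A sensitivity analysis might suffice.** The SAP allows extra ones as needed but does not commit to this one, and the main analysis would still carry the stronger assumption.

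**Conclusion.** The concern holds. As written, the main efficacy-estimand analysis of both binary AHI key secondaries is a Week 52 complete-case logistic regression. It relies on a stronger assumption than the MMRM applied to the same AHI data and need not estimate the hypothetical effect in Section 1.1.1.

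The direction of any bias is unknown. It is nil if leaving is unrelated to response. At 25% dropout it is about 0.01 to 0.07 in absolute size when poor responders leave one or both arms, and up to 0.12 only if the direction differs by arm. These sizes depend on the assumed distribution, correlation and dropout mechanism.

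There is also a cost in precision: the complete-case estimate's empirical SD was 2% to 19% larger than with suitable imputation.

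The consequence is limited. Power stays near 0.997 under the planning inputs, and the treatment regimen estimand is unaffected. This is a change that should be made, not one on which the trial's main conclusion depends.

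**What to change.** Restrict the no-imputation rule in Section 4.1.2 to endpoints analysed by MMRM. For the two binary AHI key secondaries under the efficacy estimand:

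1. Multiply impute on-treatment Week 52 AHI and ESS under MAR, separately by arm, from baseline and earlier on-treatment AHI, ESS and weight in the efficacy analysis set.
2. Impute AHI as log(AHI + 1) or by predictive mean matching, not as normal on the raw or percent scale.
3. Derive responder status in each data set, fit the planned logistic model, standardise the risk difference over all treated participants, and combine by Rubin's rules.
4. Keep the complete-case logistic model as a sensitivity analysis.

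In trial-size simulations of the composite (103 per arm, 500 trials), log-scale imputation was within 0.005 of the full-data result and predictive mean matching within 0.01.

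The cost is SAP wording and modest programming, since multiple imputation with Rubin's rules is already planned for the other estimand. The drawbacks are reliance on an imputation model for skewed AHI and little gain for participants who stop before Week 20, who have no on-treatment AHI after baseline.

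A related wording point: for the uncontrolled 10%, 15% and 20% weight-loss endpoints, Section 4.4.3 says an MMRM handles missing data while Table GPIF.4.3 specifies logistic models. The SAP should say what is meant, or impute weight in the same way.
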